8.1 Intercurrent Event 1 (IE1): Premature Discontinuation of Study Drug

Following the intent-to-treaty (ITT) principle, a treatment policy strategy will be used to handle the IE1. Data collected on/after premature discontinuation of study drug will be used for all efficacy endpoints.

The only exception is when data are collected on/after the date subjects switching to other treatment for CD, which will be handled as follows:

- **Binary endpoints other than the occurrence of hospitalization and/or the occurrence of CD-related surgery endpoints:** A composite strategy will be used in the efficacy analysis: the subject will be considered as non-responders at all visits on/after the initiation of other CD-related confounding medications.
- **Binary endpoints regarding the occurrence of hospitalization and/or the occurrence of CD-related surgery endpoints:** A treatment policy strategy will be used regardless.
- **Continuous endpoints:** A hypothetical strategy will be used in the efficacy analysis. Data collected on/after the initiation of other CD-related confounding medications will not be used in the analysis. Efficacy analysis will be handled by using corresponding statistical models (e.g., the Mixed-Effect Model Repeated Measurement [MMRM] model).

The CD-related confounding medications include:

- Biologics approved for CD (Adalimumab, Certolizumab, Infliximab, Ustekinumab, Vedolizumab, Natalizumab)
- Any investigational compound
- Systemic corticosteroids or locally acting steroids, rectal corticosteroid
- Immunosuppressants (azathioprine, mercaptopurine, methotrexate, tacrolimus, cyclosporine)

8.2 Intercurrent Event 2 (IE2): CD-Related Corticosteroids

The CD-related corticosteroids intercurrent event is defined as follows.

In Part 1/Part 2:

1. subjects not on CD-related corticosteroids (systemic or oral locally acting corticosteroids for CD) at baseline which are then initiated during Part 1/Part 2
2. a) subjects on CD-related corticosteroids at baseline who have dosages increased to greater than the prednisone equivalent dose taken at baseline until Week 10 or
b) subjects with any dose increase in CD-related corticosteroids between Week 10 and Week 12
3. subjects not on rectal corticosteroid at baseline who initiated rectal corticosteroids during Part 1/Part 2, regardless of rectal corticosteroid dose
4. subjects on rectal corticosteroids at baseline who have the dosage increased to greater than the dose taken at baseline during Part 1/Part 2;
5. subjects on rectal corticosteroids at baseline and initiated different rectal corticosteroids during Part 1/Part 2, regardless of rectal corticosteroid dose

In Part 3:

1. subjects not on CD-related corticosteroids (systemic or oral locally acting corticosteroids for CD) at baseline which are then initiated during Part 3
2. a) subjects on CD-related corticosteroids at baseline who have dosages increased to greater than the prednisone equivalent dose taken at baseline and Week 12 until Week 22 or
b) subjects with any dose increase in CD-related corticosteroids between Week 22 and Week 24

3. subjects not on any rectal corticosteroid at baseline and during Part 1/Part 2 who initiated rectal corticosteroids during Part 3, regardless of rectal corticosteroid dose
4. subjects on rectal corticosteroids at baseline or during Part 1/Part 2 who have dosage increased to greater than the dose taken at baseline during Part 3;
5. subjects on rectal corticosteroids at baseline or during Part 1/Part 2, and initiated different rectal corticosteroids during Part 3, regardless of rectal corticosteroid dose

The time point of the CD-related corticosteroids intercurrent event is defined as the date when one of the scenarios above occurs for a subject.

Binary endpoints other than the occurrence of hospitalization and/or the occurrence of CD-related surgery endpoints: A composite strategy will be used in the efficacy analysis: the subject will be considered as non-responders at all visits on/after the initiation of CD-related corticosteroids.

Binary endpoints regarding the occurrence of hospitalization and/or the occurrence of CD-related surgery endpoints: A treatment policy strategy will be used regardless.

Continuous endpoints: A hypothetical strategy will be used in the efficacy analysis. Data collected on/after the initiation of CD-related corticosteroids will not be used in the analysis. Efficacy analysis will be handled by using corresponding statistical models (e.g., the Mixed-Effect Model Repeated Measurement [MMRM] model).

9.0 Efficacy Analyses

9.1 General Considerations

The primary and secondary efficacy endpoints as specified in Section 3.0 will be analyzed based on ITT1 for Part 1. The difference between treatment groups for the primary and secondary efficacy endpoints will be tested with graphical multiplicity adjustment¹ to

ensure a strong control of family-wise type I error rate at significance level $\alpha = 0.05$ (2-sided) (see Section 12.0). Analyses of other efficacy endpoints for Part 1 will be performed using ITT1 at significance level $\alpha = 0.05$ (2-sided) without multiplicity adjustment.

No statistical comparisons will be performed for Part 2 and Part 3. For all efficacy endpoints, the descriptive statistics will be provided by treatment group for Part 1, for overall for Part 2 and by cohort for Part 3. The statistics include number of observations, mean, standard deviation, 95% CI, minimum, median, and maximum for continuous variables, and number, percent and two-sided 95% CI for discrete variables. And number of subjects with missing data due to COVID-19 pandemic will be summarized for primary and secondary efficacy endpoints.

Unless otherwise specified, any subject who is randomized based on a wrong stratum will be analyzed according to the actual stratum the subject belongs to.

The Primary Analysis will be performed after all enrolled subjects have completed Part 1, Part 2 and Part 3, and the database has been locked. This will be the only and final efficacy analysis.

"Baseline" refers to the last non-missing observation prior to the first administration of study drug in Part 1 or Part 2 or prior to the randomization if no study drug is given.

Analysis of Categorical Variables:

For categorical variables, frequencies and percentages will be reported for each treatment group in Part 1, for overall for Part 2 and for each cohort in Part 3. Comparison of upadacitinib group and placebo group will be performed using the Cochran Mantel-Haenszel (CMH) test adjusting for stratification factors (baseline steroid use (Yes, No), endoscopic disease severity ($SES-CD < 15, \geq 15$) and number of prior biologics with prior inadequate response or intolerance ($\leq 1, > 1$)). If there is a stratum for a treatment group that has no subject in it, a value of 0.1 will be added to all cells in the corresponding table in order to prevent dividing by 0, as suggested in Greenland and Robins (1985).² Point

estimates and 95% confidence intervals (CI) for the difference in proportions between upadacitinib group and placebo group will be provided. Construction of CI for the common risk difference will be based on the Mantel-Haenszel estimate adjusting for stratification factors.

For endpoints with small sample size (such as resolution draining fistulas at Week 12 in subjects with draining fistulas at Baseline) or small number of responders (e.g., occurrence of CD-related hospitalizations during Part 1), comparison of upadacitinib group and placebo group will be performed using the Chi-Square test (or Fisher's exact test if more than 20% of the cells have expected counts of less than 5).

Analysis of Continuous Variables:

For continuous variables, the model based mean and standard error will be provided. The mean value of the variable at baseline and each scheduled visit will also be presented for each treatment group. Continuous variables collected longitudinally will be using a Mixed-Effect Model Repeated Measurement (MMRM) model. Continuous efficacy variables which are collected at only one post-baseline visit (such as SES-CD) will be analyzed using an Analysis of Covariance (ANCOVA) model. Point estimates and 95% CIs of mean change from baseline within each treatment group, and the difference between upadacitinib group and placebo group will be provided.

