## Appendix G. Corticosteroid Taper

Beginning at Week 4, all subjects will undergo the mandatory taper schedule outlined below, in which all subjects continuing in the study will have corticosteroid discontinued no later than Week 11. For subjects entering the study on a corticosteroid dose that is in between two specific levels in taper schedule, the dose beginning at Baseline will be rounded up to the closest higher dose.

Baseline Dose	Prednisone or Prednisolone Dose Change at Each Study Week								
	Wk 4	Wk 5	Wk 6	Wk 7	Wk 8	Wk 9	Wk 10	Wk 11	Wk 12
30 mg/day	25 mg	20 mg	15 mg	10 mg	7.5 mg	5 mg	2.5 mg	Discontinue	0
25 mg/day	20 mg	15 mg	10 mg	7.5 mg	5 mg	2.5 mg	Discontinue	0	0
20 mg/day	15 mg	10 mg	7.5 mg	5 mg	2.5 mg	Discontinue	0	0	0
15 mg/day	10 mg	7.5 mg	5 mg	2.5 mg	Discontinue	0	0	0	0
10 mg/day	7.5 mg	5 mg	2.5 mg	Discontinue	0	0	0	0	0
7.5 mg/day	5 mg	2.5 mg	Discontinue	0	0	0	0	0	0
5 mg/day	2.5 mg	Discontinue	0	0	0	0	0	0	0
2.5 mg/day	Discontinue	0	0	0	0	0	0	0	0

Baseline Dose	Budesonide Dose Change at Each Study Week								
	Wk 4	Wk 5	Wk 6	Wk 7	Wk 8	Wk 9	Wk 10	Wk 11	Wk 12
9 mg/day	6 mg	6 mg	3 mg	3 mg	Discontinue	0	0	0	0
6 mg/day	3 mg	3 mg	Discontinue	0	0	0	0	0	0
3 mg/day	Discontinue	0	0	0	0	0	0	0	0

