3.0 Endpoints

The following endpoint definitions apply to the efficacy variables described below:

- **Clinical remission per PROs:** average daily very soft or liquid SF ≤ 2.8 AND average daily AP score ≤ 1.0 and both not greater than baseline
- **Clinical remission per CDAI:** CDAI < 150
- **Enhanced Clinical Response:** $\geq 60\%$ decrease in average daily very soft or liquid SF and/or $\geq 35\%$ decrease in average daily AP score and both not greater than baseline, or clinical remission per PROs
- **Clinical response 100 (CR-100):** decrease of at least 100 points in CDAI from Baseline
- **Clinical response per PROs:** $\geq 30\%$ decrease in average daily very soft or liquid SF and/or $\geq 30\%$ decrease in average daily AP score and both not greater than Baseline
- **Endoscopic remission:** SES-CD ≤ 4 and at least 2 point reduction from Baseline and no subscore > 1 in any individual variable, as scored by central reviewer

- **Endoscopic response:** decrease in SES-CD > 50% from Baseline of the induction study (or for subjects with an SES-CD of 4 at Baseline of the induction study, at least a 2 point reduction from Baseline), as scored by central reviewer

Details of CDAI, SES-CD and PRO questionnaires are provided in [Appendix D](#), [Appendix E](#) and [Appendix F](#) respectively.

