3.3.2 Other Endpoints for Part 2

Same efficacy endpoints as those listed in Part 1 (Section 3.1 and Section 3.2) are considered for Part 2 of the study. All the Part 2 efficacy endpoints are considered other endpoints and ranking of the endpoints is not applicable for Part 2.

3.3.3 Other Endpoints for Part 3

- Achievement of:
 - clinical remission per PROs at Week 16, Week 20 and Week 24
 - clinical remission per CDAI at Week 16, Week 20 and Week 24
 - enhanced clinical response at Week 16, Week 20 and Week 24
 - clinical response at Week 16, Week 20 and Week 24
 - CR-100 at Week 16, Week 20 and Week 24
 - Endoscopic response at Week 24
 - endoscopic remission at Week 24
 - clinical remission per PROs and endoscopic remission at Week 24
 - clinical remission per CDAI and endoscopic remission at Week 24
 - enhanced clinical response and endoscopic response at Week 24
 - corticosteroid use discontinuation for CD and clinical remission per PROs at Week 24 (population: ITT subjects taking corticosteroids for CD at Week 12)
 - corticosteroid use discontinuation for CD and clinical remission per CDAI at Week 24 (population: ITT subjects taking corticosteroids for CD at Week 12)

- corticosteroid use discontinuation for CD and endoscopic remission at Week 24 (population: ITT subjects taking corticosteroids for CD at Week 12)
- corticosteroid use discontinuation for CD and enhanced clinical response at Week 24 (population: ITT subjects taking corticosteroids for CD at Week 12)
- corticosteroid use discontinuation for CD at Week 24 (population: ITT subjects taking corticosteroids for CD at Week 12)
- corticosteroid use discontinuation for CD and endoscopic response at Week 24 (population: ITT subjects taking corticosteroids for CD at Week 12)
- $\geq 50\%$ reduction in the corticosteroid dose for CD from Baseline at Week 24 (population: ITT subjects taking corticosteroids for CD at Week 12)
- resolution of EIMs at Week 24 (population: ITT subjects with EIMs at Baseline or Week 12)
- decrease in SES-CD $> 50\%$ from Baseline or endoscopic remission at Week 24, as scored by central reviewer
- SES-CD ≤ 2 at Week 24
- SES-CD ulcerated surface subscore of 0 at Week 24 in subjects with SES-CD ulcerated surface subscore ≥ 1 at Baseline, as scored by a central reviewer
- SES-CD ulcerated surface subscore ≤ 1 in each segment at Week 24 in subjects with a SES-CD ulcerated surface subscore ≥ 2 at Baseline, as scored by a central reviewer

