- CGHAS/IGHAS histologic remission (defined as CGHAS/IGHAS score ≤ 2) at Week 24 in subjects with abnormal histology at Baseline
- $\geq 50\%$ reduction in draining fistulas at Week 24 (population: ITT subjects with draining fistulas at Baseline)
- resolution of draining fistulas at Week 24 (population: ITT subjects with draining fistulas at Baseline or Week 12)

- at least 50% decrease in the number of days with very soft or liquid stools (Type 6 or 7, per Bristol Stool Chart) during the last 7 days at Week 24.
- Occurrence of:
 - hospitalizations due to CD during Part 3
 - hospitalizations during Part 3
 - CD-related surgeries during Part 3
- Change from Baseline in:
 - IBDQ at Week 24
 - WPAI-CD at Week 24
 - EQ-5D-5L at Week 24
 - CSS at Week 24
 - FACIT-F at Week 24
 - SF-36 at Week 24
 - FCP at Week 16, Week 24
 - hs-CRP at Week 16, Week 20 and Week 24
 - average daily AP score at Week 16, Week 20 and Week 24
 - average daily very soft/liquid SF at Week 16, Week 20 and Week 24
 - average daily total SF at Week 16, Week 20 and Week 24
 - CDAI at Week 16, Week 20 and Week 24
 - SES-CD at Week 24
 - CGHAS/IGHAS at Week 24 among subjects with abnormal histology at Baseline
- Time to:
 - clinical response
 - enhanced clinical response
 - clinical remission per PROs
 - clinical remission per CDAI
 - CR-100

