10.0 Safety Analyses

10.1 General Considerations

Safety analyses will be performed on the safety population for Part 1 (SA1) and SA-UPA population as defined in Section 4.0. In addition, safety summaries will be performed on the safety analysis set for Part 2 (SA2) and Part 3 (SA3).

The standard safety analyses will include reporting of adverse events (AEs), adverse events of special interest (AESIs), laboratory, and vital signs measurements. Frequency tables and exposure adjusted event rate per 100 patient-years tables of subjects with treatment-emergent adverse events (TEAEs) by system organ class (SOC) and by preferred term (PT) as in the Medical Dictionary for Regulatory Activities (MedDRA) dictionary will be provided by treatment group. All continuous laboratory parameters and vital signs variables at each visit will also be summarized by treatment group. Frequency tables of subjects meeting criteria for potentially clinically important vital sign values and for potentially clinically important laboratory values will be provided by treatment group.

The baseline for safety analysis will be treatment dependent. For the Part 1/Part 2 laboratory and vital signs measurements, the baseline value is defined as the last available measurement before study drug administration for all subjects. Starting from the Part 3, the baseline value for subjects initially randomized to upadacitinib will remain the same. However, the baseline value for subjects initially randomized to placebo will be redefined as the last available measurement before first dose of upadacitinib administration in Part 3.

For the safety analysis, subjects are assigned to a treatment group based on the treatment actually received, regardless of the treatment randomized.

Missing safety data will not be imputed.

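### Part 3 efficacy keeps the pre-induction Baseline, so Cohort 1's Baseline-referenced results mix placebo and upadacitinib periods, and one steroid endpoint can be met by a dose reduction made wholly in Part 1

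*SAP*

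**What the plan says.** - SAP 9.1 defines Baseline for efficacy once: it "refers to the last non-missing observation prior to the first administration of study drug in Part 1 or Part 2". No other reference point is given for Part 3.
- SAP 3.3.3 lists Part 3 changes from Baseline, for example "CDAI at Week 16, Week 20 and Week 24", and likewise SES-CD, FCP, hs-CRP, stool frequency (SF), abdominal pain (AP) and the questionnaires.
- SAP 3.0 measures endoscopic response "from Baseline of the induction study (or for subjects with an SES-CD of 4 at Baseline of the induction study". CR-100 is also a fall in CDAI from Baseline.
- Under SAP 2.2, Cohort 1 consists of placebo subjects without clinical response at Week 12, whose first upadacitinib dose comes in Part 3.
- SAP 10.1 treats laboratory and vital-sign data differently. From Part 3, "the baseline value for subjects initially randomized to placebo will be redefined as the last available measurement before first dose of upadacitinib administration", while "the baseline value for subjects initially randomized to upadacitinib will remain the same".
- One Part 3 steroid endpoint in SAP 3.3.3 is a ≥50% "reduction in the corticosteroid dose for CD from Baseline at Week 24 (population: ITT subjects taking corticosteroids for CD at Week 12"). Protocol Appendix G states: "Beginning at Week 4, all subjects will undergo the mandatory taper schedule outlined below", with steroids ended by Week 11 at the latest. Protocol 5.3.1.1 (Corticosteroid Taper) nevertheless lets the taper be stopped, or the dose raised again before Week 10 up to the Baseline dose. It has an unfinished taper resume at Week 16 in Part 3.
- SAP 9.1 and 9.5 plan no comparisons for Part 3, only descriptive summaries by cohort.

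**The concern.** A stated aim of Part 3 is to offer upadacitinib induction to placebo non-responders. A reader will take Cohort 1's Week 24 results as what happened on upadacitinib. With the Baseline of SAP 9.1, those results describe 24 weeks, of which the first 12 were on placebo. The SAP recognises the issue for this cohort's safety data but has no counterpart for efficacy and gives no reason. Hematocrit and body weight show the mismatch: as safety variables they are referred to Week 12, while as CDAI components they enter a change that starts before placebo.

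The steroid endpoint has a related flaw. It selects subjects by steroid use at Week 12 but counts the reduction from the Baseline dose, so a reduction completed before Part 3 can satisfy it.

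**Working it through.** The documents give no sample size, rate or power for Part 3, so there is no stated figure to reproduce. The check is which endpoints are exposed, and how far.

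**1. Reference point by endpoint (SAP 3.0 and 3.3.3)**

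| Part 3 endpoint | Reference | Can it already be met at Week 12? |
|---|---|---|
| Clinical response, enhanced clinical response, PRO remission | Baseline, with absolute limits for remission | No (step 2) |
| Endoscopic response, CR-100 | Baseline | Yes |
| Endoscopic remission | SES-CD ≤4, and a fall of at least 2 from Baseline | Yes |
| CDAI remission, SES-CD ≤2 | Absolute | Yes, whatever the Baseline |
| Resolution of EIMs or draining fistulas | Present at Baseline or Week 12 | Yes, if resolved before Part 3 |
| Change scores | Baseline | Not applicable; both periods are mixed |
| Six steroid-discontinuation endpoints | On steroids at Week 12 | No |
| ≥50% steroid reduction | Baseline dose, in subjects on steroids at Week 12 | Yes (step 5) |

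**2. Why three symptom endpoints start at zero.** Part 3 admits only Week 12 clinical non-responders. Enhanced clinical response requires a fall of ≥60% in SF or ≥35% in AP, or PRO remission. Either fall exceeds the 30% that defines clinical response. PRO remission requires SF ≤2.8 and AP ≤1.0, with neither above Baseline. Entry required SF ≥4.0 and/or AP ≥2.0. From SF ≥4.0, reaching 2.8 is a fall of at least 1 − 2.8/4.0 = 30%. From AP ≥2.0, reaching 1.0 is a fall of at least 50%. Each of these endpoints therefore implies clinical response. Enumerating 604,038 combinations of 7-day averages that satisfy the entry criterion found none with remission or enhanced response but without clinical response.

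CR-100 is different. As an illustration with the CDAI weights, let average well-being go from 3 to 1, which gives 2 × 7 × 7 = 98 points, and SF from 6.0 to 4.5, which gives 1.5 × 7 × 2 = 21 points. The total is 119 points. SF has fallen 25% and AP is unchanged, so the subject is a clinical non-responder who meets CR-100.

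**3. Change scores, illustrative values (assumptions)**

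| Measure | Baseline → Week 12 → Week 24 | Decrease from Baseline | Decrease from Week 12 |
|---|---|---|---|
| SF | 6.0 → 4.5 → 4.2 | 30.0% | 6.7% |
| SES-CD | 16 → 10 → 7 | 56% | 30% |
| SES-CD | 16 → 7 → 7 | 56% | 0% |
| SF | 6.0 → 7.0 → 4.9 | 18% | 30% |

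In the first row, 1.5/1.8 = 83% of the decrease precedes the first upadacitinib dose. The third row is a Week 24 endoscopic responder with no change on the drug. In the fourth, the subject worsened on placebo and the Baseline reference understates the change on upadacitinib.

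**4. Size for endoscopic response.** The placebo arm has 165 subjects (SAP 2.4). If 20% to 50% respond clinically at Week 12 (assumption), Cohort 1 is at most 165 × 0.80 = 132 to 165 × 0.50 = 82.5. SAP 2.4 plans for 10% endoscopic response in the whole placebo arm. Taking 3% to 10% among clinical non-responders (assumption) gives 82.5 × 0.03 = 2.5 to 132 × 0.10 = 13.2, so about 2 to 13 subjects already in response before any upadacitinib. That is at most 3 to 10 percentage points of Cohort 1's Week 24 rate, and only if all of them still respond at Week 24.

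**5. Steroid reduction.** In every row of Appendix G the scheduled dose is at or below 50% of Baseline by Week 6. The top rows at Week 6 are prednisone 30 → 15 mg, budesonide 9 → 3 mg, methylprednisolone 24 → 12 mg and hydrocortisone 120 → 60 mg. The table below gives the non-zero prednisone doses that already meet the endpoint.

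| Baseline (mg/day) | First such dose | Reduction |
|---|---|---|
| 30 | 15 mg, Week 6 | 50% |
| 25 | 10 mg, Week 6 | 60% |
| 20 | 10 mg, Week 5 | 50% |
| 15 | 7.5 mg, Week 5 | 50% |
| 10 | 5 mg, Week 5 | 50% |
| 7.5 | 2.5 mg, Week 5 | 66.7% |
| 5 | 2.5 mg, Week 4 | 50% |
| 2.5 | none (goes straight to zero) | – |

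A subject whose taper stopped at such a dose, who was not re-escalated and who had no net reduction in Part 3, is a Week 24 success.

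**The case against.** The strongest reply is that the Baseline reference is deliberate. It keeps Week 24 on the same scale as Week 12 of Part 1, and clinical response against Baseline also governs entry to Study M14-430. Different baselines for safety and efficacy are not a contradiction, and the reset in SAP 10.1 is written only for laboratory and vital-sign data. This stands as a reason to keep the Baseline analyses, but it does not supply the missing Week 12 view for Cohort 1.

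Several stronger readings are tempting, and the documents do not support them:

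- *Part 3 results are inflated in favour of upadacitinib.* The direction is unknown, because non-responders may have worsened on placebo.
- *All Part 3 efficacy is affected.* Delayed clinical response, the stated question for upadacitinib non-responders, starts at zero for every entrant, and some endpoints use no Baseline value.
- *The Part 1 taper is credited throughout.* The six discontinuation endpoints count only subjects still on steroids at Week 12, so a taper completed in Part 1 earns nothing there.
- *Any taper stalled from Week 6 counts as success.* Re-escalated subjects may not qualify, and some low-dose rows are already at zero by Week 6. An unfinished taper is due to resume at Week 16, so no net Part 3 reduction requires a second interruption or a return to the Week 12 dose. Under SAP 8.2, an increase between Weeks 22 and 24 makes the subject a non-responder.

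Replacing Baseline by Week 12 would bring its own problems. Week 12 values are selected on non-response and so are open to regression to the mean. A percent change is undefined if Week 12 SES-CD is 0. Week 12 endoscopy may be missing because of COVID-19.

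**Conclusion.** The point holds in a limited form. For Cohort 1, Baseline-referenced change scores mix two treatment periods, and endoscopic response and CR-100 may be met before the first upadacitinib dose. One of the seven Part 3 steroid endpoints can be satisfied without any net Part 3 reduction.

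The estimate of 2 to 13 subjects rests on assumed placebo clinical response and on an assumed endoscopic response among clinical non-responders; the 10% is a planning rate for the whole placebo arm. The number affected by the steroid endpoint cannot be derived, since the documents do not say how many tapers will be stopped.

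The consequence is confined to the interpretation of descriptive Part 3 results. The co-primary and ranked secondary analyses, type I error and power do not depend on it.

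**What to change.** Keep the Baseline-referenced analyses and add to SAP 3.3.3 and 9.5:

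- For Cohort 1, change from the last value before the first upadacitinib dose (Week 12), given as absolute change where a percent change is undefined.
- For Cohort 1, the number already meeting each responder endpoint at Week 12.
- The ≥50% steroid reduction calculated from the Week 12 dose, shown beside the version from Baseline.
- A note that Week 12 values are selected on non-response, so regression to the mean is expected, and that Week 12 endoscopy may be missing because of COVID-19.

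Otherwise leave the original Baseline for Cohorts 2 and 3; it fits the delayed-response objective and agrees with SAP 10.1. The Week 12 assessments are already scheduled, so no new data are needed. The cost is a few extra descriptive rows, and some rates may look lower.

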2.4 Sample Size Determination

The co-primary endpoints are achievement of clinical remission per PROs (EU/EMA) or per CDAI (US/FDA) at Week 12 and achievement of endoscopic response at Week 12. Sample size calculation is based on the maximum sample size needed to detect treatment difference for each of the co-primary endpoints. The proposed assumptions were informed by the results of the 16-week clinical and endoscopic data of upadacitinib Phase 2 CD Study M13-740.

For EU/EMA regulatory purposes: Assuming a rate of 12% for clinical remission per PROs in the placebo group and 29% in the upadacitinib group at Week 12, a total sample size of 495 subjects randomized in a 2:1 ratio (330 subjects in the upadacitinib group and 165 subjects in the placebo group) will be adequate to detect at least a 17% treatment difference in clinical remission per PROs rates at Week 12 between the treatment groups using Fisher's exact test with at least 95% power at a 0.05 two-sided significant level.

For US/FDA regulatory purposes: Assuming a rate of 20% for clinical remission per CDAI in the placebo group and 40% in the upadacitinib group at Week 12, the same

sample size of 495 subjects will be adequate to detect at least a 20% treatment difference in clinical remission per CDAI rates at Week 12 between the treatment groups using Fisher's exact test with at least 95% power at a 0.05 two-sided significant level.

Assuming an endoscopic response rate of 10% in the placebo group and 25% in the upadacitinib group at Week 12, this sample size will be adequate to detect at least a 15% treatment difference in endoscopic response rates at Week 12 between the treatment groups using Fisher's exact test with at least 95% power at a 0.05 two-sided significant level.

In Part 2, assuming a Week 12 clinical response rate of approximately 52% among the subjects treated with upadacitinib 45 mg QD, an additional 150 subjects enrolled in Part 2 would provide adequate number of subjects achieving clinical response to be re-randomized to the maintenance portion of Study M14-430.

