9.6 Efficacy Subgroup Analyses

To evaluate the consistency of the efficacy over demographic and other baseline characteristics, subgroup analysis will be performed for the co-primary endpoints for the subgroups listed in [Table 3](#) below using ITT1.

For subgroup analysis, point estimate and 95% CI for each treatment group as well as point estimate and 95% CI for treatment differences between upadacitinib group and placebo group will be presented. No p-value will be provided. If, for a subgroup factor except age, sex and race ([Table 3](#)), any of the resulting categories has fewer than 10% of the planned study size, subgroup analyses will not be presented for that category.

Table 3. Subgroups for Efficacy Analysis

Subgroup Factor	Categories
Sex	Male, Female
Age	≤ median, > median
Age	≥ 18 years - < 40 years, ≥ 40 years - < 65 years, ≥ 65 years
Race	White, non-White
Race	White, Black or African American, American Indian or Alaska Native, Native Hawaiian or Other Pacific Islander, Asian, Multiple
Baseline fecal calprotectin	≤ 250 µg/g, > 250 µg/g
Baseline CD-related Steroids Use	Yes, No
Baseline CD-related immunosuppressant use	Yes, No
Baseline CD-related aminosalicylate use	Yes, No
Baseline CD-related antibiotic use	Yes, No
Baseline hs-CRP	≤ 5 mg/L, > 5 mg/L
Baseline CDAI	≤ 300, > 300
Baseline very soft/liquid SF	≤ median, > median
Baseline AP score	≤ median, > median
Baseline SES-CD	< 15, ≥ 15
Crohn's Disease Location at Baseline	Colonic only, Ileal only, Ileal-colonic
Body Weight	≤ median, > median
BMI	Underweight [$< 18.5 \text{ kg/m}^2$], Normal [≥ 18.5 and $< 25 \text{ kg/m}^2$], Overweight [≥ 25 and $< 30 \text{ kg/m}^2$], Obese [$\geq 30 \text{ kg/m}^2$]
Disease Duration	≤ 5 years, > 5 years
Geographic Region	North America, Western Europe, South/Central America, Eastern Europe, Asia, Other
Number of Prior Biologics Failed	≤ 1, > 1
Prior TNF Failure	1, > 1
Prior Ustekinumab Failure	Yes or No
Prior Vedolizumab/Natalizumab Failure	Yes or No

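### The 0.1 continuity rule in SAP 9.1 is unnecessary for the Mantel-Haenszel difference and, if carried into the subgroup analyses, biases small age and race categories

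*SAP*

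**What the plan says.** SAP 9.1 analyses binary endpoints by the Cochran-Mantel-Haenszel method over three two-level factors (baseline steroid use, SES-CD severity, number of failed biologics), which makes eight strata. The interval follows the same estimator: "Construction of CI for the common risk difference will be based on the Mantel-Haenszel estimate adjusting for stratification factors". For sparse strata the rule is: "If there is a stratum for a treatment group that has no subject in it", then "a value of 0.1 will be added to all cells in the corresponding table in order to prevent dividing by 0". The SAP attributes the constant to a cited methods paper.

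SAP 9.6 plans subgroup analyses of the co-primary endpoints: "point estimate and 95% CI for treatment differences between upadacitinib group and placebo group will be presented. No p-value will be provided". It sets a size floor but exempts three factors: "If, for a subgroup factor except age, sex and race", "any of the resulting categories has fewer than 10% of the planned study size, subgroup analyses will not be presented for that category". Table 3 includes an age category of 65 years and over and these race categories: "White, Black or African American, American Indian or Alaska Native, Native Hawaiian or Other Pacific Islander, Asian, Multiple". Section 9.6 does not say how the difference or its interval is to be calculated, and gives no rule for a category in which one arm is empty.

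**The concern.** The constant guards against a problem that the Mantel-Haenszel point estimate does not have, and it does so by inventing outcomes. A stratum that should contribute nothing is given a comparison between real subjects and an arm assumed to respond at 50%. The SAP's planning rates run from 10% to 40%, so 50% lies above all of them.

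In a large analysis set, empty arms hardly occur. In a small category cut into eight strata they are the norm, and the exemption in 9.6 allows age and race categories of any size to be shown. These outputs are meant to show whether efficacy is consistent. A shift that grows as the category shrinks could look like a weaker effect in the least represented groups.

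**Working it through.** **Inputs from the documents.** Constant 0.1 and Mantel-Haenszel difference (SAP 9.1); allocation "330 subjects in the upadacitinib group and 165 subjects in the placebo group" and planning rates of 12% vs 29% (remission per PROs), 20% vs 40% (remission per CDAI) and 10% vs 25% (endoscopic response), all from SAP 2.4. As a check on these inputs, Fisher's exact power with 330 vs 165 is 99.4%, 99.6% and 98.7%, consistent with the stated minimum of 95%. The point disputes no figure in the plan.

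**Assumed, because the documents do not give them.** Subgroup sizes and stratum shares. The shares used were 35% / 45% / 60% for the three factors, with a second set of 35% / 50% / 60%, constant response rates across strata, and 2:1 allocation within the subgroup.

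**Weight of a half-empty stratum.** The Mantel-Haenszel weight is w = n1·n0/(n1 + n0).
- Without the rule, n0 = 0 gives w = 0.
- With the rule, n0 becomes 0.2 and n1 becomes n1 + 0.2. For n1 = 1, w = 1.2 × 0.2/1.4 = 0.171; for n1 = 10, w = 10.2 × 0.2/10.4 = 0.196. The empty arm's rate is 0.1/0.2 = 50%.

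**Direction, at 29% vs 12%.** For a stratum holding one subject:
- one upadacitinib subject: (0.29 + 0.1)/1.2 − 0.5 = −17.5 points on average;
- one placebo subject: 0.5 − (0.12 + 0.1)/1.2 = +31.7 points on average;
- weighted 2:1: (2 × −17.5 + 31.7)/3 = −1.1 points, where the truth is +17.

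The net pull is therefore against upadacitinib, although a stratum with an empty upadacitinib arm pulls the other way.

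**Mean estimate in simulation, true difference 17 points** (shares 35/45/60, 40,000 runs per size; ranges show whether strata empty in both arms also receive 0.1):

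| Subgroup size | With the 0.1 rule |
|---|---|
| 50 | 16.2 |
| 35 | 15.0 |
| 25 | 13.5 to 13.7 |
| 15 | 9.7 to 10.2 |
| 8 | 5.2 to 6.3 |

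The unstratified difference averaged 16.9 to 17.1 throughout. With shares 35/50/60 the rule gave 16.9 (n=100), 16.1 (49), 14.7 (30), 12.4 (20), 9.7 (15) and 6.5 (10); omitting strata with an empty arm gave 17.0 to 17.9 for n=10 to 49. In that second set, at least one half-empty stratum occurred in over 97% of subgroups of 5 to 30, in 81% at 49 and in 26% at 100. With no true effect (12% in both arms), the rule averaged −5.4 (n=10), −3.7 (n=20) and −2.0 (n=30).

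**One arm wholly absent.** The chance of no placebo subject under 2:1 is (2/3)^n: 13% at n=5 and 1.7% at n=10. The rule still yields a number. Four upadacitinib non-responders in four different strata give 0.1/1.2 − 0.5 = −42 points. If the four wholly empty strata also receive 0.1 (weight 0.2 × 0.2/0.4 = 0.1 each, difference 0), the result is −42 × 0.686/(0.686 + 0.4) = −26 points.

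**Full ITT1.** No arm was empty in any stratum in 1,500 simulated trials of 495. Even if one stratum of 20 upadacitinib subjects had no placebo subject, its weight of 0.198 against a total of 330 × 165/495 = 110 would move the estimate by 0.198 × (−20.8 − 17)/110.2 = −0.07 points.

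**Populations restricted to one level of a factor.** Read literally, the rule also fires when four strata are absent by definition, as in the corticosteroid-at-Baseline population. If 30% to 50% of 495 subjects are on steroids (assumption), the estimate is multiplied by 33/33.4 to 55/55.4, a relative shrinkage of 1.2% to 0.7%.

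**The case against.** - **The subgroup link is inferred.** SAP 9.3.3, 9.3.4 and 9.4.2 refer back to 9.1 for the CMH method; 9.6 does not. This stands. A reader might conclude that the planned subgroup estimates are biased outright, but the documents support only a conditional statement: 9.1 is the only stated method for a difference, and 9.6 leaves the choice open.
- **A small-sample fallback exists.** SAP 9.1 moves to chi-square or Fisher for endpoints with few subjects, with a small subpopulation as its example. It covers the test, not the difference or its interval, and is not extended to subgroups. It is a partial answer.
- **Division by zero is a real risk.** This stands for per-stratum rates and for variance terms that divide by arm size. It does not hold for the point estimate, and omitting the stratum resolves both. The paper cited for the constant was not available; the arithmetic above does not depend on it.
- **Noise dominates in small groups.** Root mean squared error, rule vs unstratified, was 12.2 vs 11.4 points (n=50), 17.6 vs 16.3 (n=25), 22.1 vs 21.5 (n=15) and 27.6 vs 29.7 (n=8). Total error is therefore similar, and the rule does slightly better at n=8. This limits the importance of the point, but the bias remains systematic and avoidable.
- **Consistency does not rest on tiny cells.** Table 3 also has age by median, sex, and White vs non-White, which are likely to be larger. This stands.

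**Conclusion.** The rule is wrong for this estimator, and the consequence is minor. If 9.1 is applied to subgroups, the average loss on a true 17-point difference is about 1 point at n=50, 3.5 at n=25, 7 at n=15 and 11.5 at n=8, and it is negligible by n=100. If the floor is taken as 10% of the 495 Part 1 subjects (49.5), the other subgroup factors are kept where the loss is about 1 point; only exempted categories can fall below that. Sex is exempt but unlikely to be small. The sizes rest on assumed stratum shares and subgroup sizes.

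Two stronger inferences are not supported. The co-primary result is not compromised: ITT1 is essentially untouched, and restricted populations that lack whole strata shift by about 1% in relative terms. Nor does the rule reverse a true benefit on average: the mean stayed positive at every size examined at the planned rates, and a reversed sign arises only in individual small samples or when an arm is missing. No p-value attaches to the subgroup output.

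**What to change.** In SAP 9.1, delete the 0.1 rule and state that strata with no subject in either one or both arms are omitted from the Mantel-Haenszel estimate and its variance. In SAP 9.6, name the subgroup estimator: either this one, or an unstratified difference with a suitable interval (Newcombe, for example) for small categories. State that the difference is reported as not estimable when an arm has no subjects.

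The cost is a few sentences and a program switch. Omitting strata also discards subjects, which widens intervals in very small categories: at n=25 the simulated standard deviation was 19.9 points with omission against 16.3 unstratified. That comparison assumed equal response rates across strata, which favours the unstratified method, so either choice is defensible provided it is fixed in advance.
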